## 1. Background and Rationale

*Helicobacter pylori* (H. pylori) infection is highly prevalent in China and is associated with chronic gastritis, peptic ulcer disease, gastric mucosa-associated lymphoid tissue lymphoma, and gastric cancer. Increasing antibiotic resistance has reduced eradication success rates in real-world clinical practice.

Shenzhen Hospital of Southern Medical University manages more than 5,000 H. pylori tests and over 2,000 eradication treatments annually. Despite standardized training, eradication success rates remain suboptimal (<80% in internal data).

This study aims to evaluate the real-world effectiveness of commonly used eradication regimens and identify factors associated with treatment outcomes.

## 2. Study Objectives

### 2.1 Primary Objective

To determine the real-world eradication success rate of different H. pylori eradication regimens.

### 2.2 Secondary Objectives

- To identify demographic, clinical, and treatment-related factors associated with eradication success or failure.

- To compare the effectiveness of commonly used eradication regimens in routine clinical practice.

## 3. Study Design

This is a **single-center, retrospective, observational study** using routinely collected clinical data from Shenzhen Hospital of Southern Medical University.

- **Study Period:** 2016–2023
- **Study Type:** Observational
- **Time Perspective:** Retrospective
- **Sampling Method:** Non-probability, consecutive sampling
- **Intervention:** None (standard-of-care only)

No study-driven treatment or randomization will occur. All treatments are determined by treating physicians as part of routine care.

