## 5. Data Sources and Data Collection

Data will be extracted from electronic medical records (EMR), including:

1. Demographics (age, sex)
2. *H. pylori* testing method and results (C13 breath test, histology, culture, external hospital data)
3. DOB values for C13 testing
4. Comorbidities
5. Allergy history
6. Concomitant medications
7. Number of eradication attempts
8. Treatment regimen details (drug names, doses, duration, regimen abbreviation)
9. Post-treatment test results

No additional visits, tests, or procedures will be performed.

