## 9. Statistical Analysis Plan (SAP)

### 9.1 Sample Size

All eligible patients from 2016–2023 will be included. Estimated sample size: **~3,000 patients**.

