#### Univariate Analysis

- t-test for continuous variables
- Chi-square test for categorical variables

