#### Multivariate Analysis

- Multivariable logistic regression to identify independent predictors of eradication success

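### Physicians choose the regimen, but prescriber is neither listed for extraction nor used in the analysis; if regimen choice tracks the physician, the regimen comparison may be confounded and its P values too small

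*Combined protocol and SAP*

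**What the plan says.** The study is retrospective and not randomized. Section 3 describes how regimens were assigned: "All treatments are determined by treating physicians as part of routine care". Section 2.2 makes the regimen contrast a secondary objective ("To compare the effectiveness of commonly used eradication regimens in routine clinical practice"), and Section 6.2 lists it again as a secondary outcome.

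Section 5 opens its nine-item list with "Data will be extracted from electronic medical records (EMR), including". The treatment item is "Treatment regimen details (drug names, doses, duration, regimen abbreviation"; neither it nor any other item names the prescriber, clinic or department.

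Section 9.2 plans "Chi-square test for categorical variables" and "Multivariable logistic regression to identify independent predictors of eradication success". It names no covariates and plans no prescriber term, stratification, random effect or cluster-robust variance. It sets a two-sided P threshold of 0.05 and plans no confidence intervals. Section 9.1 gives "Estimated sample size: ~3,000 patients" and no power calculation.

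**The concern.** The physician is the assignment mechanism, and may also affect the outcome through counselling, patient selection and the arranging of re-tests, since Section 5 allows no study tests beyond routine care. If some physicians do better whatever they prescribe, and those physicians favour one regimen, their advantage is credited to that regimen. Patients of the same physician are then also correlated in both exposure and outcome, so an independence-based test overstates the information in the data.

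Both conditions are needed: physicians must differ in outcome, and regimen choice must track the physician. Without a prescriber code the study cannot check whether they hold, and a reader of the regimen comparison could not tell a regimen difference from a prescriber difference.

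**Working it through.** **Inputs from the documents.** About 3,000 patients (Section 9.1); two-sided test at 0.05 (Section 9.2); success below 80% in internal data (Section 1), with 80% used as a working value. The 3,000 is a count of available patients with no formula behind it, so there is no plan figure to reproduce.

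**Inputs assumed, because the documents give none.** Number of prescribers (equal caseloads of m patients), outcome ICC, regimen-choice ICC (0 = choice unrelated to physician, 1 = each physician uses a single regimen), and two equally used regimens.

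**Step 1: precision of the contrast.** Design effect = 1 + (m − 1) × outcome ICC × regimen-choice ICC. True error of a nominal 5% test = 2 × [1 − Φ(1.96/√design effect)].

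- 30 prescribers, m = 100: 1 + 99 × 0.02 × 0.3 = 1.59; √1.59 = 1.26; 1.96/1.26 = 1.55; error about 12%. Effective N = 3,000/1.594, about 1,880.
- 20 prescribers, m = 150: 1 + 149 × 0.02 × 0.3 = 1.89; √1.89 = 1.38; 1.96/1.38 = 1.42; error about 15%. Effective N = 3,000/1.894, about 1,580.

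Sensitivity to the assumptions, with outcome ICC 0.02 throughout:

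| Prescribers | Regimen-choice ICC | Design effect | SE ratio | True error |
|---|---|---|---|---|
| 20 | 0 | 1.00 | 1.00 | 5% |
| 20 | 0.1 | 1.30 | 1.14 | 8.5% |
| 20 | 0.3 | 1.89 | 1.38 | 15% |
| 30 | 0.3 | 1.59 | 1.26 | 12% |
| 40 | 0.3 | 1.44 | 1.20 | 10% |
| 10 | 0.3 | 2.79 | 1.67 | 24% |

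A beta-binomial simulation with no true regimen effect (4,000 runs per setting) agrees. For 20 prescribers at ICCs of 0.02 and 0.3, the SE ratio was 1.36 and the error of the unclustered test 0.147. Stratifying by physician brought the error back to 0.04–0.06 in every setting where physicians used both regimens.

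**Step 2: spurious difference.** Assume half the physicians achieve 85% and half 75% with either regimen, and that the first half supplies 70% of regimen A and 30% of regimen B.

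- A: 0.7 × 85 + 0.3 × 75 = 82%.
- B: 0.3 × 85 + 0.7 × 75 = 78%.
- Difference: 4 points with no regimen effect. At shares of 50%, 60% and 80% it is 0, 2 and 6 points.

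With 1,500 patients per regimen the independence standard error is √[(0.82 × 0.18 + 0.78 × 0.22)/1,500] = 1.46 points. Then 4/1.46 = 2.74, P about 0.006, so the planned chi-square test would call this artefact significant.

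**Step 3: consistency of the two illustrations.** The 85%/75% split implies an outcome ICC of 0.05²/(0.8 × 0.2) = 0.0025/0.16 = 0.016, and 70/30 use implies a regimen-choice ICC of 0.2²/(0.5 × 0.5) = 0.04/0.25 = 0.16. Step 2 is therefore milder than the ICCs used for the central cases in Step 1. The two steps show the same mechanism from two sides, and their effects should not be added.

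**The case against.** The strongest reply is that nothing in the documents shows the two conditions hold. That stands. A reader might infer that the regimen comparison is certainly biased, but if choice is unrelated to physician there is no bias and the error stays at 5%. If every physician splits patients exactly evenly, the unclustered test is slightly conservative (error 0.046 at outcome ICC 0.05).

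Other tempting readings also go too far:

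- **Larger error rates.** If each of 30 prescribers used a single regimen, 1 + 99 × ICC at outcome ICCs of 0.01, 0.02 and 0.05 gives design effects of 1.99, 2.98 and 5.95, and errors of about 17%, 26% and 42%. Nothing supports that extreme, and there no within-physician contrast exists, so a within-prescriber analysis could not help.
- **Section 1 as evidence.** The remark "Despite standardized training, eradication success rates remain suboptimal" does not say that success varies by physician or that physician practice drives it. Standardized training could equally mean uniform practice.
- **Prescriber lost for good after lock.** Section 8 says participants carry study ID codes. It does not say that the link to the hospital record is destroyed. Adding the field at extraction is simply easier.
- **Confidence intervals too narrow.** None is planned, so the issue is standard errors and P values.

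It is also fair that the Section 5 list is introduced as non-exhaustive and that the regression names no covariates, so prescriber is unplanned rather than excluded. And physician practice is arguably part of real-world effectiveness, which limits this point to the regimen comparison and the predictor model; describing each regimen's success rate is less affected. None of this supplies a way to detect or handle prescriber effects in those two analyses.

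**Conclusion.** The point holds in conditional form. Physicians choose the regimen, prescriber is not listed for extraction, and the stated tests assume independent patients. If physicians differ in success and regimen choice tracks the physician, the regimen comparison may be confounded and its P values too small. In the central cases the true error of a nominal 5% test is about 12% to 15%, and a spurious difference of about 4 points is plausible. These figures rest on assumed prescriber numbers, ICCs and success splits; only the 3,000 patients and the 0.05 threshold come from the plan. The change is worth making: the conditions cannot be checked without the field, and a clustered analysis is a better method than the one stated.

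**What to change.** 1. **Section 5:** add a coded prescriber ID and prescribing department to the extraction list, before database lock.
2. **Section 9.2, descriptive:** tabulate regimen use by coded prescriber, so that readers can see how far choice follows the physician.
3. **Section 9.2, models:** use prescriber as the cluster in the regimen and predictor models, through a random intercept or cluster-robust standard errors, with a small-sample correction if prescribers are few. Cluster-robust errors repair the variance but leave the point estimate unchanged, so step 4 is needed for confounding.
4. **Section 9.2, sensitivity:** add one analysis with prescriber fixed effects, limited to prescribers who used more than one regimen. State that regimen and prescriber effects cannot be separated for single-regimen prescribers.

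**Cost:** one more EMR field, whose completeness over 2016–2023 the documents do not state; somewhat larger standard errors, and wider intervals if these are reported; grouping of low-volume prescribers; and fewer patients in the sensitivity analysis. The models are standard in R, which the plan already names.

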## 4. Study Population

### 4.1 Target Population

Patients who underwent *H. pylori* testing and/or eradication treatment at Shenzhen Hospital of Southern Medical University between 2016 and 2023.

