### 4.2 Inclusion Criteria

- Age  $\geq$  14 years
- Underwent *H. pylori* testing and/or eradication treatment during the study period
- Diagnosis of *H. pylori* infection based on national consensus guidelines or clinically accepted methods

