## 6. Outcome Measures

### 6.1 Primary Outcome

***H. pylori* eradication success rate**, defined as a negative post-treatment test (C13 breath test, stool antigen, histology, or other accepted method) within 4–12 weeks after therapy.

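### A test alone qualifies a patient and nothing limits the regimen analyses to courses prescribed at the study hospital, so courses given elsewhere can enter the success rates selectively by outcome

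*Combined protocol and SAP*

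**What the plan says.** Section 4.1 describes the target population as patients with "testing and/or eradication treatment at Shenzhen Hospital of Southern Medical University between 2016 and 2023". Section 4.2 repeats the rule as "testing and/or eradication treatment during the study period", without naming the place of treatment. It adds a diagnosis of "infection based on national consensus guidelines or clinically accepted methods", without saying where or when the diagnosis must have been made.

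Section 5 takes from the medical record the "Number of eradication attempts" and the regimen details, with no restriction to courses prescribed at this hospital. It names "external hospital data" once, among the sources of test results. Post-treatment results are a separate item in the list, with no source given.

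Section 6.1 counts success as a negative test "within 4–12 weeks after therapy", wherever the drugs were prescribed. Section 9.1 includes all eligible patients, estimated at about 3,000. Section 9.2 sets no filter on where a course was given.

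**The concern.** A success rate for a regimen needs a denominator of courses that is fixed without regard to how they turned out. Under the entry rule, a patient treated elsewhere and tested here within the outcome window can supply a regimen, an attempt number and an outcome. Whether that patient comes may depend on the outcome, because someone still infected has a reason to seek further treatment that someone cured does not.

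The primary objective (2.1) is the success rate by regimen, and 2.2 adds a comparison between regimens. If outside courses are captured selectively, the first is shifted. The second is distorted whenever regimens differ in their share of outside courses. The logistic model in 9.2 would not repair this, because adjusting for patient factors does not undo selection on the outcome. Section 1 motivates the study by in-house success below 80%, so a shift of a few points matters to the conclusion.

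**Working it through.** The plan's only figure here, about 3,000 patients, is a count with no formula behind it, so there is nothing to reproduce. The check has a textual part and an illustrative part.

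**1. Eligibility of two patients treated elsewhere, each tested here inside the 4–12 week window**

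| | Tests positive here | Tests negative here |
|---|---|---|
| Test at this hospital (4.1, 4.2) | met | met |
| Diagnosis of infection (4.2) | met by this test | met only if an outside diagnosis is accepted |
| Outcome (6.1) | not a success | success |

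Both can enter, but the failure enters more easily. This asymmetry comes from the plan's own criteria.

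**2. Effect on a pooled success rate**

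Inputs:
- p, the true success rate: 0.80, assumed, set near the in-house figure of below 80% in section 1.
- f, the share of outside courses in the denominator: assumed.
- r, the chance that an outside cure is captured relative to an outside failure: assumed.

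Formulas:
- Observed success among outside courses: s = p·r / (p·r + 1 − p)
- Pooled rate: (1 − f)·p + f·s

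With p = 0.80 and f = 0.10, the pooled rate is 0.72 + 0.10·s:

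| r | s | Pooled rate | Bias (points) |
|---|---|---|---|
| 0 | 0% | 72.0% | −8.0 |
| 0.25 | 0.20/0.40 = 50.0% | 77.0% | −3.0 |
| 0.5 | 0.40/0.60 = 66.7% | 78.7% | −1.3 |
| 1 | 0.80/1.00 = 80.0% | 80.0% | 0 |
| 2 | 1.60/1.80 = 88.9% | 80.9% | +0.9 |

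Across the same values of r, the bias runs from −4.0 to +0.4 points at f = 5% and from −16.0 to +1.8 points at f = 20%. The pattern does not depend on p = 0.80: at f = 10% and r = 0 the bias is −7.5 points for p = 0.75 and −8.5 points for p = 0.85.

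**3. Effect on a comparison of two equally effective regimens**

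Assume p = 0.80 for both, with outside shares of 20% for regimen A and 5% for regimen B. The apparent deficit of A is (0.20 − 0.05)·(0.80 − s). Suppose half of outside failures are captured, and 25%, 10% or 5% of outside cures:

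| Cures captured | s | Apparent deficit of A |
|---|---|---|
| 25% | 0.20/(0.20 + 0.10) = 66.7% | 0.15 × 0.133 = 2.0 points |
| 10% | 0.08/(0.08 + 0.10) = 44.4% | 0.15 × 0.356 = 5.3 points |
| 5% | 0.04/(0.04 + 0.10) = 28.6% | 0.15 × 0.514 = 7.7 points |

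With equal capture the deficit is zero. If cures are captured twice as often, s = 88.9% and the sign reverses: 0.15 × (0.80 − 0.889) = −1.3 points, so A looks slightly better.

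**The case against.** A reader might infer that the plan counts outside courses and that the regimen rates are therefore biased downward. The documents do not support that. No section says such courses are counted. Section 3 describes a single-center study of this hospital's routine data, and section 1 argues from the hospital's own treatments, so an in-house reading is natural. Courses whose regimen is not in the record could not enter a regimen-specific rate anyway.

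A reader might also infer that external post-treatment results are brought in selectively. The external source is attached to testing, not to regimen details or post-treatment results, and may supply only the initial diagnosis.

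The direction is open to challenge too. Patients treated elsewhere may come for a confirmatory test and be negative. If the 4–12 week window is applied to failures as well as successes, many late referrals after an outside failure would have no usable outcome.

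Finally, in-house courses also need a post-treatment test, and returning for it may depend on outcome. The undefined unit of analysis (patient or course) is the more basic gap, of which outside courses are one consequence.

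These points stand as limits on certainty. They do not close the gap: an in-house reading is natural but not written, and the diagnosis criterion still favours the entry of failures. Section 6.1 states its window for success only, so whether late positives drop out depends on a rule the plan does not contain.

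**Conclusion.** The concern holds as a gap in the plan. Outside courses can enter the regimen success rates, and their entry can depend on outcome. Excess failures, and so rates that read too low, are the likelier result because of the diagnosis criterion, but the direction is not certain.

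The size is unknown. The illustrative ranges (a pooled rate of 72.0% to 80.9% at a 10% outside share, and a spurious difference of 2.0 to 7.7 points between equal regimens) rest wholly on assumed success rates, outside shares and capture rates. The second range covers only scenarios in which failures are captured at least twice as often as cures, so it leaves out zero and reversed bias. The case for changing the text does not depend on sign or size: as written, two analysts could follow the plan and report different regimen rates from the same records.

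**What to change.** In 4.1/4.2 and 9.2:

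- Restrict the primary outcome, the regimen comparison and the factor model to courses prescribed at the study hospital. This sets the outside share to zero and removes this bias whichever way it runs.
- Use courses given elsewhere only to count prior attempts.
- Record whether each post-treatment result is in-house or external, and repeat the regimen rates without external results as a sensitivity analysis.

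The cost is a few sentences and one extra field in the extraction. Somewhat fewer courses will be analysed, and the sensitivity analysis will leave more in-house courses without an outcome. The change does not address selective return for testing among in-house courses, which needs separate handling.

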### 4.2 Inclusion Criteria

- Age  $\geq$  14 years
- Underwent *H. pylori* testing and/or eradication treatment during the study period
- Diagnosis of *H. pylori* infection based on national consensus guidelines or clinically accepted methods

### 4.3 Exclusion Criteria

- Age  $<$  14 years
- Pregnant or breastfeeding women
- Patients deemed unsuitable by the investigator

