## 11. Study Timeline

- **May 2024 – September 2024:** Data extraction and cleaning
- **October 2024 – December 2024:** Statistical analysis and report preparation
- **January 2025 – May 2025:** Manuscript writing and academic dissemination

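### Section 4.3's open investigator-judgement exclusion permits outcome-dependent selection in a record study whose outcomes already exist; delete it or replace it with listed record-based reasons

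*Combined protocol and SAP*

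**What the plan says.** The third exclusion in section 4.3 reads "Patients deemed unsuitable by the investigator". No criteria follow it there or elsewhere.

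The setting is a retrospective review of routine records. Section 3 states "No study-driven treatment or randomization will occur" and section 5 states "No additional visits, tests, or procedures will be performed". Section 5 draws regimen details (item 8) and "Post-treatment test results" (item 9) from the same electronic medical record. Section 6.1 counts a negative test "within 4–12 weeks after therapy" as success. The first activity listed in section 11 is "Data extraction and cleaning", from May to September 2024.

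On completeness, section 3 describes "Non-probability, consecutive sampling" and section 9.1 says "All eligible patients from 2016–2023 will be included". Sections 8 and 10 provide double entry, source verification, SOP training and a check of protocol adherence. None of these provisions defines unsuitability, masks the person who judges it, or asks for a count of those excluded.

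**The concern.** A clause of this kind is familiar from prospective trials. There it can keep a patient away from study procedures that might harm them, and it acts before the outcome is known. Neither condition holds here. Treatment is over, nothing is done to the patient for the study, and the result sits in the file from which eligibility is judged.

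A judgement on unstated grounds, made when the outcome can be seen, can depend on that outcome without any intent. What is exposed is the primary eradication rate and, if exclusions differ by regimen, the regimen comparison in sections 2.2 and 6.2. A report that follows the plan need not show how many patients were removed under this clause or from which regimens.

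**Working it through.** **Timing.** The study period ends in 2023 (section 3). Therapy ended on 31 December 2023 plus 84 days (12 weeks, section 6.1) gives 24 March 2024, which is 38 days before 1 May 2024. Even a course ending on 7 February 2024 would have a closed window by 1 May. No earlier screening step is listed. The documents do not say whether the person judging suitability sees the results.

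**Inputs for size.** The plan gives about 3,000 patients (section 9.1, with no precision or power derivation to reproduce) and success below 80% (section 1). It gives no number of discretionary exclusions. Assumed here: n = 3,000 evaluable, although not all of the 3,000 need be evaluable, and true success p = 75%, range 70–80%.

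**Single rate.** Half-width = 1.96 × √(p(1−p)/n) = 1.96 × √(0.75 × 0.25/3000) = 1.55 points (1.64 at 70%, 1.43 at 80%). After k exclusions, of which a share f are failures, the observed rate is (np − k(1−f))/(n − k). There are 2,250 successes and 750 failures.

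| Excluded | Who is excluded | Observed rate | Shift (points) |
|---|---|---|---|
| 60 (2%) | unrelated to outcome (f = 0.25) | 2205/2940 = 75.00% | 0 |
| 60 (2%) | half failures | 2220/2940 = 75.51% | +0.5 |
| 60 (2%) | all failures | 2250/2940 = 76.53% | +1.5 |
| 60 (2%) | all successes | 2190/2940 = 74.49% | −0.5 |
| 150 (5%) | failures twice as likely | 2160/2850 = 75.79% | +0.8 |

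In the last row, 4% of successes (90) and 8% of failures (60) are removed.

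The half-failures row is not a mild case. It removes 30/750 = 4.0% of failures against 30/2250 = 1.3% of successes, so failures are three times as likely to be excluded. The ratio is 2.3 at 70% success and 4 at 80%. Over 70–80% success, the half-failures shift is 0.4 to 0.6 points and the all-failures shift 1.4 to 1.6.

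To exceed the 1.55-point half-width takes 61 exclusions (2.0%) if all are failures: 2250/2939 = 76.56%. It takes 176 (5.9%) if half are: 2162/2824 = 76.56%.

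**Comparison of two regimens.** Assume 500 patients in each, both truly 75% (375 successes, 125 failures). The half-width of the difference is 1.96 × √(2 × 0.1875/500) = 5.4 points. Removing failures from one regimen only, with a pooled two-proportion z-test:

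- 10 removed (2%): 375/490 = 76.5% against 75.0%, p = 0.57
- 25 removed (5%): 375/475 = 78.9% against 75.0%, p = 0.14
- 35 removed (7%): 375/465 = 80.6% against 75.0%, p = 0.035

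The last case discards 35/125 = 28% of one regimen's failures and none of its successes.

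**The case against.** The strongest reply is that this is a stock catch-all and no harm is shown. Consecutive sampling and the inclusion of all eligible patients signal an intent to take everyone, which makes large discretionary removal less plausible. That stands as a point about likelihood. It does not close the gap, because who counts as eligible depends on this very clause. The adherence check in section 10 does not close it either, since an exclusion made under the clause adheres to the protocol. The SOPs mentioned there might contain an exclusion log, but they are not part of the documents.

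A second reply is that the clause can remove duplicate or uninterpretable records. This also stands. A reader might infer that the clause serves no purpose at all, but the absence of study procedures removes only a participant-safety purpose. The data-quality purpose remains, and a list of objective reasons would meet it.

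A third reply is that moderate selection has little effect. That is right on the figures: with failures twice as likely to be excluded, losing 5% of patients moves the rate by 0.8 points, inside the half-width.

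**Conclusion.** The concern holds as a design weakness that should be corrected. Section 4.3 allows undefined exclusions at a time when outcomes already exist, and nothing in the plan limits them. Confidence is high on the text and moderate on the impact.

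Two stronger readings are not supported. A reader might infer that the results will be biased upward; the documents show the opportunity, not the event, and preferential exclusion of successes would bias the rate downward. A reader might also infer that small exclusions could readily create a difference between regimens; under the assumed 500 per regimen, only extreme one-sided removal does so.

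The true size is unknown. Under the assumed 3,000 evaluable patients and 75% success, a 2% exclusion moves the primary rate by anything from 0 to 1.5 points upward, depending on how many of those excluded are failures, against a half-width of 1.55.

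**What to change.** Preferred: delete the third exclusion in section 4.3. This is a one-line change that needs no masking or staged extraction. The cost is that a few messy records stay in.

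Alternative: replace it with a short list of objective, record-based reasons, for example duplicate record or no identifiable regimen. Apply the list before post-treatment results are viewed, and report exclusions per reason by regimen, with a row for regimen unknown. This costs more. Extraction must be staged so that eligibility is fixed before outcome fields are opened. Section 5 item 2 does not separate pre- from post-treatment tests, so a date filter or some record review is needed. Masking would be only partial for patients with repeat attempts, because a later attempt suggests that the earlier one failed.
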